The following baseline assessments will be completed prior to administration of study drug:

- Review of medical history
- Although the risk of serious side effects is low when diclofenac is applied to the skin, pregnant women will be excluded from this study. Urine pregnancy screening will be conducted for all female subjects of childbearing potential.* Women who have a positive pregnancy test would be excluded.
- Limited skin examination and blood pressure measurement. We will exclude patients with SBP > 160 and DBP > 95 at screening.
- Collect pain information such as onset, pain intensity 24 hours prior and immediately before study drug application

*Female subjects are considered "of child-bearing potential" if they (a) are anatomically and physiologically capable of becoming pregnant and (b) they will be, or could possibly be, engaging in sexual activity with males while study interventions that pose the possibility of harm to a fetus are occurring. Note that this time period also includes any time after study activities have ended where the protocol specifies the use of contraception.

Dose, Delivery and Dispensing

After obtaining consent, subjects will be randomized to one of two study groups (Bonipar or diclofenac topical solution 1.5%), utilizing a predetermined randomization schedule in a 1:1 ratio.

The study drug, Bonipar, is stored in an opaque plastic bottle so that the contents may be protected from both direct and indirect sunlight because it is likely that sunlight could result in the degradation and/or decomposition of some of the essential oils contained in Bonipar. For blinding purposes, Diclofenac topical solution 1.5% will be stored in the same opaque plastic bottle. The bottles will be labeled either "Drug A" or Drug B" according to their designation, lot #, BUD (beyond use dating), dosing instructions, and FDA statement "Caution: New Drug—Limited by Federal law to investigational use". Thus, the drugs would be blinded to both the patients and to the investigators. Only the unblinded Clinical Research Coordinator (CRC) will have access to the randomization scheme and will have the knowledge of the dispensed drugs. To avoid any bias, the principal investigator would strongly advise the study technicians not to communicate any information regarding the 2 drugs to their investigator colleagues.

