All subjects will be instructed on the application of the assigned drug. Subjects will be asked to apply the study drug 2 pumps 2 times a day to be applied topically on the affected area during a one week treatment period. Application instructions will be provided to the subjects. Prior to the first use, the study coordinator will prime the pump by pushing down fully 4 times, and to discard any solution to ensure an accurate dose is delivered during first use.

Study Drug Application at Home

Written study drug application instructions, storage instructions, and a study diary will be provided to all subjects at the time of discharge from the clinic.

At home, subjects will continue to apply the study drug twice a day. In the 1 week diary, subjects will record daily drug application, pain scores before and after application and any other oral pain medication taken. Subjects are permitted in the study to take acetaminophen (325 to 650 mg tablet up to 4 times a day) if pain persists even with the study drug application.

Subjects will be instructed to observe the following instructions:

1. Please wash and dry hands before and after use.
2. Do not apply to skin with open wounds, or blistered or inflamed areas of the skin.
3. Avoid contact with your eyes and mucous membranes.
4. Do not apply external heat.
5. Do not shower for at least 30 minutes after applying study drug.

6. Do not wear clothing over the treated area until the area is dry.
7. Do not take other NSAID (like aspirin, ibuprofen, naproxen, ketorolac, diclofenac, etc.) while enrolled on this study. Please contact the study doctor or research staff if you are unsure.
8. Keep the bottle away from direct sunlight.
9. Protect the treated area from natural or artificial sunlight.
10. Wait until the treated area is dry before applying sunscreen, insect repellent, lotion, moisturizer or cosmetics to the same area.
11. Avoid skin-to-skin contact between other people and the treated area until the treated area is completely dry.

Follow- Up

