- Include a thorough description of how risks and discomforts will be minimized (per 45 CFR 46.111(a) (1 and 2)). Consider physical, psychological, legal, economic and social risks as applicable. If vulnerable populations are to be included (such as children, pregnant women, prisoners or cognitively impaired adults), what special precautions will be used to minimize risks to these subjects? Also identify what available alternatives the person has if he/she chooses not to participate in the study. Describe the possible benefits to the subject. What is the importance of the knowledge expected to result from the research?

Herbal products have been used relatively safe for years with very few adverse effects. FIDAPIN, a topical analgesic with similar essential oil components as Bonipar (except for one herbal oil), had been studied in a randomized double-blind placebo controlled trial in 196 subjects with chronic musculoskeletal pain involving Fidapin (n=64), Diclofenac ointment (n=67) and a placebo (Jasmine oil, n=65). All groups showed a significant decrease in pain after 2 and 4 weeks. Both the diclofenac (4 subjects) and placebo group (2 subjects) developed adverse events (superficial rashes) while those receiving Fidapin did not experience any adverse effects or complications. The superficial rashes receded after discontinuation of the therapy. One subject on the diclofenac group had a progressive radicular pain and paresthesia – that subsided when it was discontinued after 8 days of use. Another observation was that Fidapin had a relatively rapid onset of action.

Since Bonipar is a topical analgesic made from naturally-occurring essential oils, the risk of developing any systemic adverse effects is highly unlikely. There is a small possibility that some patients may develop

cutaneous reactions, e.g. rashes, skin irritation etc. If such reactions were to occur, the study would be immediately halted for that subject and treatment would be offered at no costs to the patient. All subjects will have a skin examination on the treated area at baseline (before treatment). The area will be examined for the presence of the following: skin discolorations, hyperemia, skin elevations, scratch marks, wheals, pruritus, bruises, hair pattern, skin effusions and presence of any abnormal skin characteristics. AEs, if any, will be recorded at the follow-up study visit and the patient may be asked to return if the PI deems it necessary.

Costs to the Subject

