1. The success rate will be 52% among diclofenac topical solution 1.5%vs. 62% true success rate among Bonipar group (with -10% non-inferiority margin)
2. The success rate will be 52% among diclofenac topical solution 1.5%vs. 67% true success rate among Bonipar group (with -10% non-inferiority margin)

Difference $D_0 = P_2 - P_1$ (non-inferiority margin)

$H_0: P_2 - P_1 \leq D_0$

$H_1: P_2 - P_1 = D_1 > D_0$

D_1 : True observed difference i.e. $P_1(H_1) - P_2$

Where P_1 & P_2 represent the proportion of success for Bonipar and diclofenac topical solution 1.5% group respectively.

Statistical power and required sample size for the aforementioned two scenarios are presented in the table.

| Power | Alpha | D_0 | D_1 | P_2 | $P_1(H_0)$ | $P_1(H_1)$ | N_1 | N_2 | Total N |
|-------|-------|-------|-------|-------|------------|------------|-------|-------|---------|
| 0.80 | 0.05 | -0.10 | 0.10 | 0.52 | 0.42 | 0.62 | 76 | 76 | 152 |
| 0.80 | 0.05 | -0.10 | 0.15 | 0.52 | 0.42 | 0.67 | 49 | 49 | 98 |

Pass software was used to determine sample size of the study. With a sample size of 152 (76 per group), we will be able to achieve 80% statistical power to detect a difference in success rate on pain reduction of 10% between Bonipar and diclofenac topical solution 1.5% groups with a non-inferiority margin of 10%. If we consider a 10% drop out rate, we will need to enroll 8 more patients per group a total of 168. This 10% drop out rate did not reflect the patient population. Consequently, we plan to consent 240 subjects in order to reach our target goal of 152 completed subjects.

Interim Analysis:

After approximately 50% of the study is completed (75 to 95 patients), we plan to carry a preliminary statistical analysis of the patients who have completed the study at that time.

We do NOT plan to analyze the primary data i.e. the pain scores of the two groups because that process could potentially interfere with the non-inferiority integrity of the final analysis of that data.

We are therefore proposing on the advice and approval of our Consultant Statisticians:

- 1) to analyze all the data as one group and not to differentiate between the group receiving the study drug and the group receiving Diclofenac.
- 2) to analyze the secondary data including adverse effects and dropout status from the study and to perform a comparative analysis between the two groups.

Data & Safety Monitoring

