- Summarize safety concerns, and describe the methods to monitor research subjects and their data to ensure their safety, including who will monitor the data, and the frequency of such monitoring. If a data monitoring committee will be used, describe its operation, including stopping rules and frequency of review, and if it is independent of the sponsor (per 45 CFR 46.111(a) (6)).

There is no plan for formal data and safety monitoring board. Given the small target size for enrollment, we do not feel that a formal DSMB is necessary. However, all adverse events should be immediately reported to the principal investigator, [name]. The principal investigator will report any adverse and serious adverse events to the IRB during the study. PI will review and sign off on all adverse events on a weekly basis. All adverse events will be reported to the FDA at the end of the study.

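### Adverse events are not actively sought from subjects who stop early, and the baseline skin checklist has no stated post-treatment counterpart

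*Combined protocol and SAP*

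**What the plan says.** Two sections of the combined protocol and SAP describe how adverse events enter the record.

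- **Risk/Benefit Assessment:** "AEs, if any, will be recorded at the follow-up study visit", with a further return visit at the principal investigator's discretion.
- **Data & Safety Monitoring:** "all adverse events should be immediately reported to the principal investigator", with weekly sign-off by that investigator.

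The skin is examined before treatment. Baseline Assessments lists "Limited skin examination and blood pressure measurement". The Risk/Benefit Assessment then itemises the features to look for, such as discoloration, wheals and bruising. No later skin examination is stated.

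For cutaneous reactions the Risk/Benefit Assessment says: "If such reactions were to occur, the study would be immediately halted for that subject", and treatment is offered free of charge.

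Study Drug Application at Home gives the diary contents: "In the 1 week diary, subjects will record daily drug application, pain scores before and after application and any other oral pain medication taken".

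Follow-Up asks all subjects back at one week and allows a video visit. Its assessments are not itemised. Subjects without adequate relief may drop out and are asked to discard the remaining drug. Nothing is said about asking them for adverse events.

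Adverse effects are the third listed outcome measure. Data Analysis & Statistical Considerations says side effects will be looked at between the groups, without naming an analysis population.

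**The concern.** Rashes and skin irritation are the main risk the plan names for the study product, and whether one product irritates more than the other is a between-arm question. The answer is only as good as the collection of events.

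As written, collection has one scheduled point, the 1-week visit. Before then it relies on subjects volunteering information. A subject who develops a mild reaction, stops applying the product and does not get in touch may leave no record of it. If one product irritates more, such losses would fall more heavily on that arm and narrow the observed difference.

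Separately, the baseline skin checklist can show a change only if something is set against it later, and the plan states no such examination.

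**Working it through.** **Does immediate reporting close the gap?** The rule in Data & Safety Monitoring says where a known event goes. It does not say how staff come to know of one. Sources during the treatment week are:

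| Possible source | What the plan provides |
|---|---|
| Diary | Applications, pain scores, oral pain medication; no adverse-event item listed |
| Eleven home-use instructions | None asks the subject to report a skin reaction; the only prompt to contact staff concerns NSAIDs |
| Contact at early withdrawal | None described |
| 1-week visit | Adverse events recorded; skin examination not stated |
| Payment | $30 after the 1-week visit and return of the diary, so it gives an early leaver who skips the visit no incentive |

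Home-use instruction 2 tells subjects not to apply the product to blistered or inflamed skin. A subject who reacts can follow it by simply stopping, with no stated step that informs staff.

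**How many subjects might stop early?** The plan gives no figure for the safety comparison, so its enrolment figures are the starting point. The 76 per group comes from the Power Calculation (52% vs 62%, margin 10 points, one-sided alpha 0.05, power 80%). With the pooled-variance Z formula:

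n = [1.645 × √(2 × 0.57 × 0.43) + 0.842 × √(0.52 × 0.48 + 0.62 × 0.38)]² / (0.62 − 0.52 + 0.10)² = 75.5, rounded up to 76.

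This agrees with the plan. It matters here only as the number of completers per arm.

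The plan states: "we plan to consent 240 subjects in order to reach our target goal of 152 completed subjects".

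- Not completing: 240 − 152 = 88
- Share: 88/240 = 36.7%
- Per arm, if split evenly (assumption): 88/2 = 44

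Consent comes before the eligibility checks and randomisation, so the 88 may include people who never received study drug. Treated subjects per arm therefore lie between 76 (every treated subject completes) and 120 (every consented subject is treated).

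**How many rashes might be expected?** The Risk/Benefit Assessment cites a trial of a related product with rashes in 4 of 67 on diclofenac ointment, 2 of 65 on placebo and 0 of 64 on the related product. Assuming the diclofenac rate carries over:

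- Rate: 4/67 = 6.0%
- 76 treated: 76 × 4/67 = 4.5
- 120 treated: 120 × 4/67 = 7.2

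**How many might go unrecorded?** The documents do not give this share, so the whole range is shown for 120 treated:

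| Share unrecorded | Rashes recorded |
|---|---|
| 0% | 7.2 |
| 25% | 5.4 |
| 50% | 3.6 |
| 75% | 1.8 |
| 100% | 0 |

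At the other end, 76 treated means no treated subject leaves early, so loss through quiet leavers is nil by construction. The missing skin comparator remains in either case.

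**The case against.** A reader might infer that, because subjects with skin reactions are taken off study, the safety comparison misses the very patients most likely to have events. The documents do not support that. Staff can halt a subject and offer treatment only once they know of the reaction, and a known reaction must be reported at once. Follow-Up asks all subjects back at one week, with a video option. The final side-effect comparison is not restricted to completers. The interim analysis is described as covering patients who have completed, but it also compares dropout status.

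The two recording statements can also be read as compatible: continuous reporting, plus a systematic record at the visit. The Risk/Benefit Assessment does not say events are recorded only then. The diary form itself is not in the documents, and the 1-week assessments are not itemised, so part of the concern rests on silence. Blinding limits expectation-driven differences in reporting. The rash rate comes from an ointment trial assessed at 2 and 4 weeks, whereas this trial uses a 1.5% solution for one week. There is no secondary objective and no formal safety hypothesis.

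Most of this stands, and it removes any claim that events are known to be lost. It does not answer the narrower point. Subjects who stop without telling staff are reached by neither the halt rule nor the reporting rule. No withdrawal contact is described. The skin checklist has no stated post-treatment counterpart.

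**Conclusion.** The concern holds as a gap in how adverse events are elicited, not as an established loss of events. Under the stated schedule, capture before the 1-week visit depends on unprompted reports, and the baseline skin findings have nothing stated to be compared with.

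The size cannot be fixed from the documents. The 36.7% is an upper bound on non-completion among treated subjects, because it is counted from consent. The 4.5 to 7.2 expected diclofenac rashes assume that the related-product trial's rate applies to a different formulation and a shorter period. The unrecorded share could be anywhere from none to all, and the halt and reporting rules point towards the low end for reactions severe enough to be noticed and reported. A reader should not take any single figure, such as half the rashes lost, as a finding. With counts this small, however, a few missed events could alter the comparison: two of 7.2 is 28%.

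This is a modest improvement, worth making because it is cheap.

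**What to change.** 1. Reconcile the Risk/Benefit Assessment with Data & Safety Monitoring under one rule: adverse events are recorded whenever they are reported, and are also asked about at the 1-week visit and by phone or video when a subject withdraws.
2. Add an adverse-event and skin line to the diary.
3. Repeat the Risk/Benefit Assessment's skin checklist at the existing 1-week visit, on camera if the visit is remote.
4. State in Data Analysis & Statistical Considerations that side effects are compared in all treated subjects.

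The cost is one diary line, one short call per dropout and about a minute at a visit that already takes place. These changes concern data collection and analysis only; no treatment rule changes.

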All subjects will be asked to come back for a study visit at one week (+/- 1 day) after initial dosing for assessment, to return the completed diary and remainder of the study drug. If subjects are not able to physically return for the follow-up visit, a remote video follow-up visit can be done for the required study assessments. Remote visits will not be audio or video recorded. Subjects completing a remote video follow-up visit must return to clinic for a physical follow-up visit when able. Subjects who do not receive adequate pain relief during the study may opt to drop out and resume taking their prior prescribed medications or they may return to their primary care physician. If this occurs, subjects will be asked to discard any unused study drug.

DURATION OF STUDY:

This study will be for 1 weeks from initial study drug application.

OUTCOME MEASURES:

The following assessments would be determined:

1. Numerical Pain Rating Scale (NPRS) score at:
 - a. time of enrollment
 - b. 24-hours earlier
 - c. 1 week later twice daily (am and pm)
2. Time of Onset of Action of Bonipar measurement
3. Report of any adverse effects or complications.

Protected health information (PHI) will be kept confidential as required by law. Some information collected about this research study may be kept in a research study record separate from the medical record, and some research information may also be part of the medical record. Except when required by law, subject will not be identified by name, social security number, address, telephone number, or any other direct personal identifier in study records disclosed outside of Duke University Health System (DUHS). For records disclosed outside of DUHS, subject will be identified using a unique code number. The unique code and date of birth will be reported on the Case Report Forms (CRF). The key to the code will be kept in a locked file.

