- Describe and justify any costs that the subject will incur as a result of participation; ordinarily, subjects should not be expected to pay for research without receiving direct benefit.

There will be no additional costs as a result of being in this study. Bonipar and diclofenac topical solution 1.5% will be provided free of charge for use in this study.

Data Analysis & Statistical Considerations

- Describe endpoints and power calculations. Provide a detailed description of how study data will be analyzed, including statistical methods used, and how ineligible subjects will be handled and which subjects will be included for analysis. Include planned sample size justification. Provide estimated time to target accrual and accrual rate. Describe interim analysis including plans to stop accrual during monitoring. Phase I studies, include dose escalation schema and criteria for dose escalation with definition of MTD and DLT.

The primary objective of the study is to evaluate the reduction in acute and chronic musculoskeletal pain by Bonipar in comparison to conventional treatment of diclofenac topical solution 1.5%. Pain responses at base line and at two-week follow up will be measured in the scale of 0 to 10, where 0 indicates no pain and 10 indicates highest level of pain. For each patient, primary outcome variable will be measured in two ways: i) compute whether the decrease in pain by 50% between baseline and 1-week follow-up (i.e. binary variable) and, ii) calculate the absolute difference in pain score between baseline and 1-week follow-up (continuous variable). Statistical power and sample size was determined based on the binary outcome variable.

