Initial data characteristics will be compared between groups using chi-square for categorical variables and t-test or Wilcoxon rank sum test for continuous variables. Change in pain from baseline will be compared between two treatment groups using chi-square test for binary variable and t-test or equivalent non-parametric test for continuous variable, as appropriate. The significance level of the test will be targeted at $\alpha=0.05$ (one sided). Non-inferiority will be established, at the 0.05 significance level if the lower limit of equivalent two-sided 90% confidence interval for the difference in success rate is above non-inferiority margin. Multivariable linear regression analysis will be performed to examine the changes in pain score adjusting potential confounders such as type of pain (lumbar vs. other), prior duration with pain. Reports of side effects will also be investigated between two groups. As an exploratory analysis we will evaluate the time to onset of action between two topical drugs, where time to onset variable will be measured within 1 hour (as \leq 15 min, \leq 30 min, \leq 45 min or \leq 60 min) after the application of drugs at clinic. No adjustments will be made for the multiple endpoints testing. All analyses will be conducted using SAS version 9.4.

Analysis will be performed for the full datasets and by pain group (acute and chronic).

Power Calculation:

Preliminary data to base on power analysis

Meta-analysis from Massey et al (Cochrane Database Syst Rev.; (6) 2014) presented data from combined three studies comparing topical diclofenac versus placebo (Joussellin 2003; Predel 2004; Rowbotham 2003). A total of 319 participants were treated with topical diclofenac, and 307 with placebo. The success rate (i.e. patient reported pain relief at least 50%) was 52% (166/319, range 39% to 92%) for group treated with diclofenac and 25% (77/307, range 8% to 36%) for placebo group.

Assumptions behind power calculations:

There will be two equal-sized treatment arms, one containing diclofenac topical solution 1.5% treated patients and the other Bonipar treated patients. The arms will be compared for a difference in success rate (i.e. pain reduction at least 50% from baseline to follow-up at 1 weeks) with Z-test (one-sided at alpha=0.05) using PASS software. Two scenarios will be considered, as follows:

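### The continuous form of the primary outcome is compared between arms without adjusting for baseline pain; naming baseline NPRS in the regression already planned, and letting it lead, is a free but modest gain in precision

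*Combined protocol and SAP*

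**What the plan says.** All of this is in the combined protocol and SAP, mostly under Data Analysis & Statistical Considerations.

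- The primary outcome has two forms. One is a responder variable (pain reduced by half at week 1). The other is continuous: "calculate the absolute difference in pain score between baseline and 1-week follow-up (continuous variable").
- The continuous form is compared between groups by "t-test or equivalent non-parametric test for continuous variable, as appropriate". No covariate is attached.
- A further model is planned: "Multivariable linear regression analysis will be performed to examine the changes in pain score". Its covariates are introduced only by way of illustration, in the words "adjusting potential confounders such as type of pain (lumbar vs. other), prior duration with pain". Baseline NPRS is not among the two examples given. The order of this model and the t-test is not stated.
- Sample size rests on the responder variable: "Statistical power and sample size was determined based on the binary outcome variable". So does the non-inferiority rule, which requires that the lower limit of the 90% "confidence interval for the difference in success rate is above non-inferiority margin".
- Under Baseline Assessments and Outcome Measures, pain intensity is recorded before the first application, so the covariate already exists. Under Design & Procedures, patients may enter with pain of any intensity, so baseline scores may vary widely.

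**The concern.** A t-test on change scores amounts to fixing the slope of week-1 score on baseline at 1. Pain scores usually regress towards the mean, and a patient who enters at 2 cannot fall by 5, so the slope is likely to be below 1. A model that includes baseline estimates the slope and removes the variance that the fixed value leaves behind.

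At stake is the width of the interval for the difference in mean NPRS change. As the plan stands, the named between-group comparison leaves out a baseline score recorded before the first application, and the model that could use it does not name it.

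**Working it through.** **1. The plan's own figure, to see what it depends on.** Inputs from Power Calculation: success rates 0.52 (diclofenac) and 0.62 (Bonipar), margin -0.10, one-sided alpha 0.05, 76 per arm. Distance from the margin: 0.62 - 0.52 + 0.10 = 0.20. With the null variance taken at 0.42:

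- SE under the null = sqrt((0.42×0.58 + 0.52×0.48)/76) = 0.0806
- SE under the alternative = sqrt((0.62×0.38 + 0.52×0.48)/76) = 0.0799
- Power = Φ((0.20 - 1.645×0.0806)/0.0799) = Φ(0.84) = 0.80

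The stated 76 per arm reproduces. No SD or correlation of pain scores enters it, so nothing below can change it.

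**2. Formulas for the continuous form.** Let s be the baseline SD, k the ratio of week-1 SD to baseline SD, and r the correlation between the two scores.

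- Variance of the change score: s²(1 + k² - 2rk)
- Residual variance after adjusting for baseline: s²k²(1 - r²)
- Difference between them: s²(1 - rk)²

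The product rk is the slope of week-1 score on baseline. The difference is never negative and is zero when the slope is 1. These are large-sample formulas. With 76 per arm, the one degree of freedom spent on the covariate is negligible.

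**3. Equal SDs (k = 1).** The ratio of adjusted to unadjusted variance simplifies to (1 + r)/2. The 90% half-width is 1.645 × sqrt((2/76) × variance). Here r = 0.3 to 0.7 and s = 2 points are assumptions; s affects only the half-widths, not the percentages.

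| r | Variance ratio | CI narrower by | Half-width, t-test | Half-width, adjusted |
|---|---|---|---|---|
| 0.3 | 0.65 | 19.4% | 0.63 | 0.51 |
| 0.5 | 0.75 | 13.4% | 0.53 | 0.46 |
| 0.7 | 0.85 | 7.8% | 0.41 | 0.38 |

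**4. Unequal SDs.** The result is sensitive to k.

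| k | r | Slope rk | Variance ratio | CI narrower by |
|---|---|---|---|---|
| 0.8 | 0.3 | 0.24 | 0.502 | 29.1% |
| 0.8 | 0.7 | 0.56 | 0.628 | 20.8% |
| 1.2 | 0.3 | 0.36 | 0.762 | 12.7% |
| 1.2 | 0.7 | 0.84 | 0.966 | 1.7% |
| 1.3 | 0.7 | 0.91 | 0.991 | 0.5% |
| 1.4 | 0.7 | 0.98 | 1.000 | 0.0% |

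The lower end therefore depends on where k and r are stopped, and it reaches nil within plausible values.

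**5. Bounded scale.** Trials were simulated under no treatment difference: 40,000 per setting, 76 per arm, scores rounded and clipped to 0-10, and r = 0.3, 0.5 and 0.7 before clipping. With means falling from 5.5 to 3.5, the variance ratios were about 0.64, 0.73 and 0.83. With means falling from 4.5 to 1.5 (31% of week-1 scores at zero), they were about 0.52, 0.59 and 0.66. One-sided type I error of the adjusted analysis stayed at 4.9% to 5.2% against a nominal 5%.

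**6. What is not computed.** Every ratio above compares adjustment for baseline alone with the unadjusted t-test. The gain over the planned regression, which already carries pain type and prior duration, would need the correlations among these variables, and the documents do not give them. Nor do the ratios apply to the non-parametric test.

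**The case against.** The strongest reply is that nothing the trial will decide depends on this. Non-inferiority is declared only on the success rate, no margin is set for the mean NPRS difference, and a t-test of change is valid under randomisation. In addition, the plan already has an adjusted regression whose covariate list is open, and baseline pain is an obvious candidate for it. All of this stands, and it keeps the point minor. What remains is that the continuous change is one of the two stated forms of the primary outcome, its named between-group comparison is unadjusted, and the regression neither names baseline nor is given the lead.

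Three stronger readings are tempting, and the documents support none of them.

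- *That baseline adjustment is excluded, or the result biased.* The list is introduced as examples, so baseline is unnamed rather than ruled out. With randomised arms, omitting it costs precision only.
- *That the trial is too small for the continuous measure.* A variance ratio can be turned into an equivalent number of patients, but the trial was not sized on this measure, and any such number would reflect the chosen values of k and r.
- *That the whole 8% to 19% would be gained over the analysis as planned.* It is a gain over the t-test only.

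A doubt about linear regression on a bounded 0-10 score is reasonable, but the simulated settings gave no reason to avoid it.

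**Conclusion.** The point holds as an optional improvement in efficiency. Relative to the unadjusted t-test, and assuming equal SDs and a correlation of 0.3 to 0.7, including baseline NPRS narrows the 90% interval for the mean difference in change by about 19% to 8%. The gain is larger if scores are less variable at week 1 than at baseline, and it vanishes as the slope of week-1 score on baseline nears 1. All of these inputs are assumed. The validity of the unadjusted comparison, N = 152, the stated power and the non-inferiority decision are unaffected.

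**What to change.** In Data Analysis & Statistical Considerations, state that the planned linear regression of NPRS change is the main analysis of the continuous measure. Its covariates are treatment arm, baseline NPRS, pain type and prior duration, all fixed in advance. Take as baseline the same pre-application score that is used to compute the change. With that score in the model, using change or week-1 NPRS as the outcome gives the same treatment effect. Keep the unadjusted t-test or the non-parametric test as a sensitivity analysis.

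The cost is two or three sentences and one degree of freedom for a score already collected. Data collection, N, the margin, eligibility and the success definition stay as they are.

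Which recorded scores count as baseline and as week 1 is not fully fixed in the documents, and Data Analysis & Statistical Considerations also mentions a two-week follow-up once. Those matters define the binary outcome as well, so they should be raised as a separate point and not settled through this change.
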